7. SELECTION AND WITHDRAWAL OF SUBJECTS

7.1 Subject Inclusion Criteria

1. Males and females with Fontan physiology who participated in the FUEL trial or, if they did not participate in FUEL, those who are 12 to less than 19 years of age at enrollment.
2. Participant consent or parental/guardian consent and participant assent
3. Participant fluent in English or Spanish
4. Current anti-platelet or anticoagulant therapy

7.2 Subject Exclusion Criteria

1. Height < 132 cm.
2. Weight < 40 kg.
3. Hospitalization for acute decompensated heart failure within the last 12 months.
4. Current intravenous inotropic drugs.
5. Undergoing evaluation for heart transplantation or listed for transplantation.
6. Diagnosis of active protein losing enteropathy or plastic bronchitis within the last three years, or a history of liver cirrhosis.
7. Known Fontan baffle obstruction, branch pulmonary artery stenosis, or pulmonary vein stenosis resulting in a mean gradient of > 4 mm Hg between the regions proximal and distal to the obstruction as measured by either catheterization or echocardiography.
8. Single lung physiology.
9. Maximal VO₂ less than 50% of predicted for age and gender at enrollment.
10. Severe ventricular dysfunction assessed qualitatively by clinical echocardiography within six months prior to enrollment.
11. Severe valvar regurgitation, ventricular outflow obstruction, or aortic arch obstruction assessed by clinical echocardiography within six months prior to enrollment.
12. Significant renal, hepatic, gastrointestinal or biliary disorders that could impair absorption, metabolism or excretion of orally administered medications.
13. Inability to complete exercise testing at baseline screening.
14. History of PDE-5 inhibitor use (with the exception of FUEL participation) within 3 months before study onset.
15. Use of any other drug to treat pulmonary hypertension within 3 months before study onset.
16. Known intolerance, including hypersensitivity or allergy history, to oral udenafil or any components of the investigational product.
17. Frequent use of medications or other substances that inhibit or induce CYP3A4.
18. Current use of alpha-blockers or nitrates.
19. Ongoing or planned participation in another research protocol that would either prevent

successful completion of planned study testing or invalidate its results.

- 20. Noncardiac medical, psychiatric, and/or social disorder that would prevent successful completion of planned study testing or would invalidate its results.
- 21. Cardiac care, ongoing or planned, at a non-study center that would impede study completion.
- 22. For females: Pregnancy at the time of screening, pregnancy planned before study completion, or refusal to use an acceptable method of contraception for study duration.
- 23. Unable to abstain or limit intake of grapefruit juice during the duration of the trial.
- 24. Refusal to provide written informed consent/assent.
- 25. In the opinion of the primary care physician, the subject is likely to be non-compliant with the study protocol.
- 26. History of clinically significant thromboembolic event, as adjudicated by study Investigators that may put the subject at increased risk of a subsequent event while participating in the study.

7.3 Recruitment/Enrollment Procedures

All subjects enrolled in the FUEL Trial will be offered participation in the FUEL Extension Trial. This number is anticipated to be approximately 400 subjects. If recruitment from the FUEL subjects is less than 300, additional subjects will be identified through the review of clinical data records at each participating PHN and auxiliary site. Those who are interested will be enrolled and consented at the first study visit by the study coordinator from each participating site. We plan to continue to screen and identify potential subjects until enrollment is completed. If consent is obtained for study participation but a subject is excluded on the basis of safety labs or a pregnancy test (Section 5.2), an additional subject will be recruited to replace the excluded subject.

7.4 Indications for Discontinuation of Study Drug

Study drug may be discontinued temporarily or permanently, but subjects should remain in the trial and complete all study data collection and follow-up measures, including exercise performance testing. Study drug may be discontinued for the following reasons:

- An adverse experience including failure to tolerate study medication that, in the judgment of the investigator or primary physician requires drug discontinuation.
- Voluntary discontinuation of study drug by subject.

When possible, the subject will undergo an exercise test, EndoPAT®, and echocardiogram before permanent discontinuation of the study drug. All information regarding any temporary stop and restart of study drug will be recorded.

7.5 Subject Withdrawal from Study

The “Week 52” testing will be obtained whenever possible on subjects who withdraw early. The reason for withdrawal will be documented for all subjects withdrawn from the study. A subject may be withdrawn from trial participation for the following reasons:

- Subject (or legal guardian) declines further study participation.
- Lost to follow-up despite repeated, multiple attempts by the site investigator and study coordinators to contact the subject.
- In the investigator’s or other physician’s judgment, it is in the subject’s best interest.

If the subject refuses to continue with the study visits, every attempt will be made to continue contact by telephone, written communication, or record review to determine if outcome events (death, hospitalizations and major complications) have occurred, unless the subject specifically refuses such follow-up. If the withdrawing subject is unwilling to have his/her medical records reviewed until the end of the study period (to document vital status and cause of death), he/she must submit a written refusal.

8. TREATMENTS TO BE ADMINISTERED

8.1 Description of Study Treatments

All enrolled subjects will receive udenafil at a dose of 87.5 mg twice daily for the duration of the study.

8.2 Concomitant Medications

Subjects will be treated with other medications at the discretion of their physicians. At study visits, current medications will be recorded on the study forms. If a subject begins open-label use of any other PDE-5 inhibitor at any time during the study, withdrawal from study drug is required.

The following drug interactions have been observed with PDE-5 inhibitors including udenafil:

- Medications or other substances that strongly inhibit CYP3A4 including but not limited to erythromycin, indinavir, nelfinavir, clarithromycin, fluconazole, itraconazole, nefazodone, ketoconazole, posaconazole, and voriconazole.
- Medications or substances that strongly induce CYP3A4 including but not limited to carbamazepine, phenobarbital, phenytoin, rifabutin, rifampin and St. John's Wort.
- Alpha blockers
- Intravenous inotropic drugs
- Bosentan
- Ritonavir
- Medications with a drug interaction that should be avoided:
 - Boceprevir
 - PDE-5 inhibitors other than udenafil
 - Telaprevir
 - Organic nitrates including isosorbide dinitrate, isosorbide mononitrate and nitroglycerin
 - Soluble guanylate cyclase (sGC) stimulators

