At Week 52, the subject will undergo testing for primary and secondary efficacy endpoints. Testing for this visit will include an exercise test, an echocardiogram, EndoPAT®, BNP, quality of life questionnaires and safety labs. To minimize any potential effect of the timing of administration of the study drug on testing outcomes, the time of the study drug dosing on the visit day will be standardized. Additionally, if a subject is unable to achieve a maximal effort on exercise testing, they will be offered the opportunity to repeat the EST within two weeks (14 days) of the first test. During this time period, the subject should remain on udenafil. If they achieve a maximal effort on this second study, the results of the second study will be used in the analyses.

At Week 52, vital signs (Resting Blood Pressure/Heart rate) will be obtained; assessment of adverse events, concomitant medications, drug accountability and a blood sample will be drawn for determination of udenafil and metabolite concentration immediately following the exercise test. For female subjects, serum or urine pregnancy test will be administered.

Telephone Contact (Between Baseline and Week 52)

Study coordinators will call each subject the day after drug initiation to ensure the study drug is well tolerated. Subjects will be called at weeks 1, 2, 3, 4, 8, 13, 17, 21, 30, 34, 39, 43, 47 to monitor

adherence, to collect medical history data, and record adverse events through 52 weeks. They will also be called 30 and 90 days after Week 52 to record adverse events. Subjects will be encouraged to notify the study coordinator between scheduled contact dates with any new onset symptoms or complications.

Post-Week 52 Follow-up

Option 1: discontinuation of study drug

If a participant chooses to discontinue study drug after Week 52, a study coordinator will call the subject at 30 (week 56) and 90 days (week 64) to record any additional adverse events possibly or probably related to study drug that may have occurred in the 90 days following completion of the study protocol.

Option 2: continuation of study drug for up to 36 additional months

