Following the Week 52 visit, participants will have the option of continuing on in FUEL-Extension for up to 36 months. During this time, safety data will be collected. Participants will be contacted by the study coordinator on a quarterly basis to monitor and record adverse events. Once study drug has been discontinued (maximum of 36 months following Week 52), subjects will be contacted at 30 days and 90 days following cessation of study drug to monitor for additional adverse events after discontinuation of drug.

For participants who have completed the 24-month extension and have stopped taking study drug for any period of time prior to re-consenting to version 6, the only testing needed prior to re-initiating study drug is a pregnancy test for female participants.

Table 1. Schedule of Events

Visit Number	1	1	TC1	TC 2-15	2	TC 16-17	TC 16 - 28	
Subject Status	New subject (no FUEL)	Former FUEL subject				Post week 52 Option 1	Post Week 52 Option 2	
Time point	Screening/ Baseline Day 0	Screening/ Baseline Day 0	Day 1	Weeks 1, 2, 3, 4, 8, 13, 17, 21, 30, 34, 39, 43, 47	Week 52	Day 30, 90 post-study (Weeks 56 and 64)	Quarterly	Day 30, 90 post-drug discontinue
Visit Window(s)				± 3 days	± 10 days	± 10 days		
Type of Visit(s)	In-Person	In-Person	Call	Calls*	In-Person	Calls	Calls	Calls
Informed Consent/Assent	X	X						
Subject ID# assigned	X							
Inclusion/Exclusion Criteria	X							
Physical Measurements	X							
Medical history	X							
Demographics/expanded demo	X							
Prior/Concomitant Meds	X			X	X			
EndoPAT®	X				X			
Serum or urine pregnancy test	X	X			X			
Clinical Laboratory tests (creatinine, ALT, AST)	X				X			
Biomarker (BNP) sample	X				X			
Genetic repository sample (optional)	X							
Heart Monitor (optional)	X							
Echocardiogram	X				X			
Exercise test (EST)	X ^a				X ^a			
Dispense Open Label Udenafil ^b	X	X						
Resting BP and HR ^c	X	X			X			
Administer first dose of study drug ^c	X	X						
Peds QL generic and cardiac modules; PCQLI; HAES	X				X			
Drug Accountability ^b	X				X			
Pregnancy counseling (if appl)	X	X		X				
Adverse events assessment		X	X	X	X	X	X	X
Morisky Scale (MMAS)				X				
Schedule/Confirm next visit	X	X	X	X	X			

^a If failed 1st exercise test, exercise testing can be repeated w/in 14 days. Pregnancy testing must also be repeated.^b For detailed Drug Accountability procedures, consult the Manual of Operations (MOO)^c For specific timing of procedures, see Additional Procedures and Measurements in Table 2

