6.5 Data Collection

1. Demographic information

The following demographic data will be collected: age, gender, race, ethnicity, cardiac anatomy, date of Fontan, presence of a fenestration, degree of atrioventricular valve regurgitation, grade of ventricular function, concomitant medications, and significant comorbidities.

2. Safety data

Adverse events will be reviewed with each subject at each study visit and during telephone encounters. These events will be recorded and graded by severity and relationship to study drug based on established criteria. Two additional telephone encounters will take place 30 days and 90 days following cessation of study drug [either at Week 52 or up to Week 208 if the subject opts to continue study drug] to assess for any adverse events possibly or probably related to study drug in the period following the completion of study procedures.

3. Exercise stress test

Data from the braked cycle ergometry exercise stress tests will be collected according to protocol established in the PHN Fontan Cross-Sectional Study³.

4. Assessment of ventricular performance

Each study echocardiogram will be stored in a de-identified manner and sent to a core laboratory, which will perform the data analysis and submit the measurements to the PHN Data Coordinating Center (DCC).

5. Vascular function testing

De-identified data from EndoPAT® testing will be collected according to a standardized protocol. These data will be sent to a vascular core lab, which will perform the analysis and submit the measurements to the PHN DCC.

6. Biomarkers

Serum for measurement of BNP level will be sent to a core clinical lab. Results will be sent directly to the PHN DCC.

7. Quality of life survey

Results of the Quality of life surveys will be submitted to the PHN DCC.

8. Samples for the biorepository

Samples collected for the biorepository will be shipped directly to the biorepository for future analysis.

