9. SAFETY ASSESSMENTS

9.1 Safety Considerations and Monitoring

The site study coordinators will contact each subject the day after the baseline visit, then weekly for four weeks and monthly until 52 weeks (12 months), and then at 30 and 90 days from the week 52 visit. If the subject is continuing into the extension of up to an additional 36 months then the site study coordinators will contact each subject quarterly until the subject discontinues study drug. At withdrawal or discontinuation, site study coordinators will contact each subject at 30 and 90 days from withdrawal or discontinuation to record adverse events.

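### Starting another PDE-5 inhibitor requires udenafil to be stopped at any time, but no medication check is scheduled after Week 52

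*Combined protocol and SAP*

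**What the plan says.** Section 8.2 sets the rule: "If a subject begins open-label use of any other PDE-5 inhibitor at any time during the study, withdrawal from study drug is required". The same section says "At study visits, current medications will be recorded on the study forms". It also lists organic nitrates and sGC stimulators among drugs to avoid, without a mandatory stop.

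Table 1 has a row headed "Prior/Concomitant Meds". It is marked at the new-subject baseline, on the calls from Week 1 to Week 47, and at Week 52. The columns for the Option 1 calls, the Option 2 quarterly calls and the calls after drug discontinuation are blank.

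Dosing need not end at Week 52. Section 6.5 allows it "up to Week 208 if the subject opts to continue study drug". For that period Section 6.4 (Option 2) says: "Participants will be contacted by the study coordinator on a quarterly basis to monitor and record adverse events". Subjects who completed the 24-month extension, stopped study drug and then re-consent to version 6 may restart it. For them Section 6.4 says "the only testing needed prior to re-initiating study drug is a pregnancy test for female participants".

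Two other places bear on the point. Exclusion 14 in Section 7.2 bars PDE-5 inhibitor use outside FUEL in the 3 months before entry. Section 8.4 leaves off-label use of such a drug after study completion to the subject and the primary cardiologist.

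**The concern.** A rule that obliges the site to stop the drug works only if someone asks the question that triggers it. In year 1 the question is on the schedule repeatedly. After Week 52 the dose and the rule are unchanged, but the question disappears from the schedule sites follow.

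Three things are at stake:

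- **Subject safety.** A subject could take two PDE-5 inhibitors together for some time before the mandatory stop is applied.
- **Restart of study drug.** A subject who was off udenafil may have been put on another drug of the class in the meantime. The restart paragraph does not forbid a medication history, but it does not ask for one.
- **Interpretation of the longer-term safety report** (Secondary Aim 5, Section 10.1.2). Section 6.3.3 names current medication use as a factor to relate to safety outcomes, and the causality criteria in Section 9.2.2 weigh non-study drugs. No routine medication record would exist for this period.

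**Working it through.** **1. Length of dosing after Week 52.** Section 6.5 gives Week 208 as the latest end of dosing; Section 6.4 gives up to 36 months after Week 52.
- 208 − 52 = 156 weeks.
- 36 × 52/12 = 156 weeks, so the two sections agree.

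**2. Table 1, read column by column.** The adverse-event row is a control: it fills all three columns after Week 52, so the blanks in the medication row are not a column shift from text extraction.

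| Column | Medications | Adverse events |
|---|---|---|
| Baseline, new subject | X | |
| Baseline, former FUEL subject | | X |
| Day 1 call | | X |
| Weeks 1–47 calls | X | X |
| Week 52 | X | X |
| Option 1, days 30 and 90 | | X |
| Option 2, quarterly | | X |
| Option 2, days 30 and 90 after drug | | X |

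**3. Whether the text fills the blank.** Sections 6.4, 6.5 and 9.1 describe contacts after Week 52 as adverse-event contacts. Section 8.3 adds adherence assessment and the Morisky scale, both about study drug. None of these schedules a medication question.

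**4. Scheduled checks in year 1.** The listed calls are Weeks 1, 2, 3, 4, 8, 13, 17, 21, 30, 34, 39, 43 and 47, which is 13.
- With Week 52: 13 + 1 = 14 checks; with baseline for new subjects, 15.
- Longest gap: 30 − 21 = 9 weeks.
- Table 1 numbers these calls TC 2–15, which is 14 numbers, and Section 9.1 describes contact "then weekly for four weeks and monthly until 52 weeks (12 months"). If a Week 26 call was meant but not listed (an assumption), the counts are 15 and 16 and the longest gap is 5 weeks.

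**5. Scheduled checks after Week 52.** There are 0 over up to 156 weeks. The calls that could carry one number 156/13 = 12. If the 13 numbers TC 16–28 include the day 30 and day 90 calls, the number is 13 − 2 = 11.

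**6. Share of an opt-in subject's dosing time after the last scheduled check.**
- 12 extra months: 12/24 = 50%.
- 24 extra months: 24/36 = 67%.
- 36 extra months: 36/48 = 75%.
- Subjects who stop at Week 52: 0%.

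**7. Effect of marking the quarterly calls.** The wait from starting a second PDE-5 inhibitor to a scheduled question would be at most about 13 weeks. It would average about 13/2 = 6.5 weeks if start dates are spread evenly. As marked now, no scheduled question follows.

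**The case against.** The strongest reply is that a blank in Table 1 does not prove that an item is omitted. Dispensing is marked only at baseline, yet Section 8.3 provides courier resupply. Drug accountability is marked only at the new-subject baseline and Week 52, yet 8.3 calculates tablet consumption bi-monthly. The Morisky scale is unmarked for Option 2, yet 8.3 puts it on the quarterly calls. Nor are the statements in 6.4 about the purpose of calls complete. The year-1 text gives only "adherence, to collect medical history data, and record adverse events through 52 weeks", although Table 1 marks medications on those calls.

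This weakens any argument from the table alone. But in each of the three table examples the protocol text supplies what the table lacks. Here the only candidate is the recording sentence in 8.2, and only if study visits includes telephone calls. Table 1 does list calls under type of visit, so that reading is possible. Against it, Section 6.5 separates study visits from telephone encounters. On the wider reading the requirement exists and Table 1 contradicts it, which still needs correcting.

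Other limits stand. Quarterly contact continues, and a new drug could emerge when adherence is discussed or through the record review in Section 9.2.3. Exclusion 21 makes it plausible that the study center's cardiology team would know of the prescription. Section 8.4 concerns use after study drug stops, so it bears on the restart group and does not show concurrent use. The percentages above measure time without a scheduled check, not harm.

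**Conclusion.** The concern holds. From Week 52 to as late as Week 208, a mandatory stop has no scheduled question behind it: 0 marked checks in up to 156 weeks, against 14 to 16 in year 1 depending on the reading. Detection is not impossible, but it rests on incidental routes, so the stop could come late.

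The scope is limited to subjects who opt to continue and to the longer-term safety report. How many opt in, and how often another PDE-5 inhibitor is started, are not stated, so no number of affected subjects can be given. The conclusion rests on the schedule and text as written. The Manual of Operations, to which Table 1 refers for drug accountability, was not available and might add a check. The point is worth correcting because the gap concerns a safety rule and closing it costs little.

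**What to change.** - In Table 1, mark the medication row in the Option 2 quarterly column, with a direct question on other PDE-5 inhibitors, nitrates and sGC stimulators. The last two go beyond the mandatory stop but are already on the 8.2 list of drugs to avoid.
- In Section 6.4, Option 2, state that medications are recorded at each quarterly call.
- In the restart paragraph of Section 6.4, add a medication review beside the pregnancy test.
- In Section 8.2, say that medications are recorded at study visits and at scheduled calls, so that it matches Table 1.
- As clerical tidying, make Table 1 and Section 8.3 agree on when the Morisky scale is given, and reconcile the 13 listed year-1 calls with the 14 call numbers.

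The cost is a table and wording amendment, plus a few minutes on each of the existing quarterly calls and a short review at any restart. No new visit or procedure is needed.

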8.3 Procedures for Monitoring Subject Adherence

Study drug adherence will be assessed at each scheduled study contact by the study coordinator. Additionally, adherence will be calculated bi-monthly by comparing the expected versus actual consumption of study drug tablets. The study coordinator will remind the subject to return study drug bottles to the site during each call contact. Each subject will receive via traceable courier a resupply of study medication. Subjects will have the option to return all remaining study drug from previous supply to the site using a pre-paid envelope from a service provider with the capability to track the shipment (e.g. FedEx or UPS). The study coordinator or pharmacist will measure and record the number of remaining tablets. Once the pill count is complete, the pharmacy may then destroy the returned study medication according to standard operating procedure.

The study coordinator or pharmacist will measure and record the number of remaining tablets, and a study drug supply will be dispensed. Once the pill count is complete and the study drug has been monitored, the pharmacy may then destroy the returned study medication according to standard operating procedure.

Self-report of study drug compliance will be assessed with administration of the Morisky scale²⁴. The Morisky scale is a questionnaire used to predict adherence to medication therapies. The scale will be administered during each quarterly contact call.

